STUDY PROTOCOL

Effect of probiotics on T2DM and pre-diabetes in China ---the role of gut microbiota composition

Background

According to recent surveyed, diabetes prevalence rate in Chinese adults had gone up to 11.6%, the pre-diabetics diabetes prevalence rate was 50.1%. Effective intervention is urgently needed. Study of relationship between intestinal flora and diabetes is a hot topic at present. Gut microbiota disorders may be involved in the development of diabetes by means of increasing the number of inflammatory mediators, chronic inflammation, insulin resistance, increased energy intake, and obesity ect. In view of the correlation between gut microbiota and diabetes, gut microbiota can be taken as an important target for diabetes intervention. In this study, we aim to explore whether probiotics intervention affect blood glucose level and Risk factors for diabetes in T2DM and pre-diabetes via modification of gut microbiota composition and other post-interventional effects.

Objectives :

1. To investigate the effects of probiotics intervention on blood glucose metabolism (blood glucose, insulin sensitivity) and diabetes risk factors (blood lipid, weight, body composition, inflammatory state) in diabetes and pre-diabetes.
2. To investigate the effect of probiotics intervention on gut microbiota composition and its correlated metabolite.
3. To investigate the mediating effect of gut microbiota on glucose control in diabetes and pre-diabetes.

Methods/design

Trial design

This is a four-arm randomized controlled trial (Diabetes-intervention n=30, Diabetes-control n=30, prediabetes-intervention n=80, prediabetes-control n=80) . Participants are recruited from the outpatient registration pool of those who have participated in annual health checks for diabetes during 2017 to 2018 at Health care Center, Southwest Hospital, Chongqing, China. After an initial screening, potential subjects will be assessed for inclusion in the run-in trial. Those subjects who meet the inclusion criteria will be then invited to the intervention study for a total duration of 3 month. Those participants who are qualified for the intervention study will be randomized into intervention or control group after baseline assessments.

Eligibility criteria

Inclusion criteria:

1. The patient was diagnosed with pre-diabetes or diabetes by OGTT
2. Age: 18-60y
3. BMI:18-35kg/m²

Exclusion criteria:

1. Patients who have diabetes, hyperlipemia , and need regular use of drugs.
2. Secondary obesity or diabetes.
3. Serious systematic diseases, such as digestive diseases, tumor, cardiac, pulmonary, renal, rheumatic and immune system diseases.
4. Pregnant women, women ready for pregnancy, and nursing mothers.
5. Take antibiotics or bacterial agents within 1 month
6. Diarrhea or abscess in 1 month or blood or other abnormal feces
7. Diabetics history more than 2 years
8. The OGTT experiment $FG \geq 9 \text{ mmol/L}$ or $2h \geq 14 \text{ mmol/L}$ in diabetic patients

Study settings

The interventions and laboratory tests and performed and managed at the Health Care Center, Southwest Hospital, Chongqing, and Health management institute, PLA General hospital, Beijing, China.

Trial design

Interventions

1. Probiotics group: Diabetes/prediabetes participants take four packs of probiotics a day on an empty stomach with 200ml water every morning. The probiotics is called KAWAI, each pack contains 880 billion dead *Lactobacillales* (*S. thermophilus*) .
2. Placebo group:
Diabetes/prediabetes participants take four packs of probiotics a day on an empty stomach with 200ml water every morning.

Primary and secondary outcomes

Primary outcomes:

1. Blood glucose levels(FBG and OGTT), insulin sensitivity(Insulin, C-peptide)
2. Gut microbiota composition

Secondary outcomes:

1. Blood inflammatory markers
2. Diabetes risk factors (blood pressure, blood lipids)
3. Weight, waist circumference, BMI, Body composition
4. Intestinal endocrine function (GPL-1)
5. Gut microbiota metabolites

The primary and secondary outcome measures will be assessed at baseline, 1- and 3-month time points.

Measurements procedures

1. Screening:

The potential subjects will be selected from the outpatient pool of those who have records of abnormal blood glucose level in 2017. Registered nurses from health care center will first contact the potential subjects and invite them to a

study information meeting. Detailed information of the objectives of the study, its nature and constraints, the anticipated risks and the expected benefits are given by the investigating physician of endocrinology and professor of sport medicine in the recruitment information meetings. When the screening consent form has been signed, patients will be asked to fill in a screening questionnaire to check their health and medication background as well as alcohol consumption, and to undergo a glucose tolerance test (blood draw after overnight fasting, followed by samples of 2 hours after the intake of 75 g of glucose).

Follow-up visits

The purpose of the follow-up visits is to monitor the compliance, enhance retention of the subject in the study, and obtain information on factors that may affect outcomes of the study. A study coordinator will contact participants every month to check their oral probiotics records. The study coordinator will also give feedback. The participants will have follow-up visits to the laboratory of Health care Center, Southwest Hospital, Chongqing at months 1, 3. Their height, weight, blood pressure, blood samples, fecal samples, and changes in health status and body composition will be checked at those time points.

Methods of measurements

1. Questionnaire, anthropometry and physical examinations

Background information regarding lifestyle, behavioral and motivational characteristics as well as medical history will be collected by questionnaires. Data gathered from eligible subjects will then be used to describe the study populations, and individual results will be used to screen the changes and for monthly feedback.

Height will be determined using a wall-fixed measuring device, and weight using a calibrated scale. Height and weight will also be used to determine body mass index (BMI, weight(kg)/(height(m))²). Blood pressure will be measured after 5 min rest. A physician will examine the physical conditions of subjects and ensure that subjects meet the inclusion criteria.

2. Blood samples

Glucose tolerance tests will be performed after overnight fasting and 2 hours

after the intake of 75 g glucose for the assessment of serum insulin, and glucose. Venous blood samples will be taken in standardized fasting conditions at 7–8 a.m. Total cholesterol, high-density lipoprotein (HDL), low-density lipoprotein (LDL), triglycerides, will be measured from serum sample by conventional methods. ELISA can be used to assess serum samples for adiponectin, tumor necrosis factor alpha (TNF α), C-reactive protein (CRP), interleukin (IL-6), interleukin 10 (IL-10), and lipopolysaccharides (LPS). Gut microbiota metabolites will be measured from serum sample by LC-MS/MS.

3. Fecal samples collection

The fecal samples (two samples per each time) will be collected in the health care center during the second day of the 3-day dietary records collection. The study will provide to subjects the materials for sample collection. The subjects are advised to sample approximately 2–3 grams of feces by spatula attached to the cover of the plastic specimen jar. Fecal samples are frozen after collection within 30 min, stored at -80°C . 16SrDNA sequencing will be performed. Different bacterial indices will be calculated to evaluate the interrelationship of different bacterial species and how they are associated with diabetes.

4. Body composition

Bioelectrical impedance analysis will be used to estimate lean tissue mass (LM), fat mass (FM) and bone mass (BM) of the whole body, legs, arms, and trunk as well as android and gynoid regions.

Concomitant adherences and procedures

To ensure good compliance in probiotics and placebo group, we will keep in contact with them via phone call monthly questionnaire to check on their physical condition and lifestyle at 1 and 3months follow-up during the intervention.

Sample size estimation

The sample size calculation with an estimate of how many participants will be needed for the primary outcome to be statistically, clinically and/or politically significant. For the specific primary outcome of blood glucose and microbiota, based on our pilot study, 68 prediabetes subjects in each group would have 85% power for mean comparison between the randomized groups for the fast

blood glucose. We set the significance level at 0.05 and allowed for 10 mean comparisons with the Bonferroni correction between the groups. Taking into account the compliance and drop-out (15%), we increase our sample size to 80 in each prediabetes group. With the same approach, sample size for each diabetes group is 60 subjects.

Randomization methods

1. Randomization Process:

SPSS will be used for generating the randomization assignment for Diabetes groups and prediabetes groups respectively. Randomization numbers will be generated and sealed in an envelope and kept by the study coordinator. On the basis of subjects' enrolment time when 20 qualified subjects are reached, the study coordinator will open one block to allocate subjects into each group.

2. Blinding:

Both subjects and investigators will be blinded with respect to the randomization assignment of each participant. The investigators will remain blinded until the completion of the study. The study coordinator will be blinded from which group the participants are signed in. The accuracy of the randomization log is the responsibility of the study coordinator.

Statistical methods

All data collected by questionnaires will be entered into database management software (EpiData), double checked by independent researchers, and exported to SPSS statistics version. If data is not normally distributed, their natural logarithms will be used for further analysis.

Descriptive statistics will be used to present the background and anthropometric data at the baseline and follow-up assessments as mean and 95% confidence interval (CI) unless otherwise stated.

An intention-to-treat (ITT) analysis will be performed to compare the Probiotics group to Placebo group. The effects of the interventions will be assessed using analysis of variance (ANCOVA) for repeated measures (treatment group \times time) and baseline difference as a covariate. If the significance of the group by time interaction is $p < 0.05$, the effect will be localized utilizing Bonferroni for multiple comparisons. The level of statistical significance chosen for the contrasts will be $p < 0.05$. In addition to the ITT

analysis, efficacy or active treatment analysis will be done when the compliance of the participation of the intervention is $\geq 60\%$ of the whole trial [ANCOVA for repeated measures (treatment group \times time) and baseline difference as a covariate.] The percentage differences (0–3month) will be calculated from duration between baseline and end point measurements for each individual. The comparison of percentage changes in different groups will be performed using ANCOVA (two factor interactions: compliance/noncompliance \times treatment group) controlled for the baseline value using Bonferroni for multiple comparisons. If the significance of the overall group difference is $p < 0.05$, then the effect will be localized by contrast to the Con group. When the 95% CI does not include zero, the difference is regarded as statistically significant at $\alpha = 0.05$.

Linear Pearson's correlation, partial correlation, Kendall Tau's, and bivariate, logistic, and multivariate regression analysis will be used for analysing relationships. In addition, systems biology approaches will be used to develop models which integrate the different types of data and the high-throughput data measured in terms of gut microbiota composition, as well as LPSs and inflammation.

Ethical issues, research permits or information permit applications

The current study will continue to adhere to all relevant guidelines for good scientific and clinical practice. All subjects in this study are volunteers. None of the measurements are known to have any significant health risk.

The benefits and associated risks of the study will be carefully explained to the subjects and voluntary participation will be stressed. Informed consent will be obtained from all subjects. The study physician will be available during the laboratory tests. The study has been approved by Ethics Committee of PLAGH, (S2016-068-01).

All data will be handled and archived confidentially. All image scans and background information will be electronically transferred and stored in the specific database. The blood samples and fecal samples will be stored at -80°C . If the analyses will be performed outside the data collection site, the sample transportation will be handled according to the relevant safety standards. The duration of the sample storage is generally 10 years. If the samples storage time exceeds the permitted time, a new permit will be obtained from both the subjects and the Ethical committee. If the subjects are deceased, permission will be sought from the relatives.

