## Statistical plans

All data collected by questionnaires will be entered into database management software (EpiData), double checked by independent researchers, and exported to SPSS statistics version. If data is not normally distributed, their natural logarithms will be used for further analysis.

Descriptive statistics will be used to present the background and anthropometric data at the baseline and follow-up assessments as mean and 95% confidence interval (CI) unless otherwise stated.

An intention-to-treat (ITT) analysis will be performed to compare the Probiotics group to Placebo group. The effects of the interventions will be assessed using analysis of variance (ANCOVA) for repeated measures (treatment group  $\times$  time) and baseline difference as a covariate. If the significance of the group by time interaction is  $p < 0.05$ , the effect will be localized utilizing Bonferroni for multiple comparisons. The level of statistical significance chosen for the contrasts will be  $p < 0.05$ . In addition to the ITT analysis, efficacy or active treatment analysis will be done when the compliance of the participation of the intervention is  $\geq 60\%$  of the whole trial [ANCOVA for repeated measures (treatment group  $\times$  time) and baseline difference as a covariate.] The percentage differences (0–3month) will be calculated from duration between baseline and end point measurements for each individual. The comparison of percentage changes in different groups will be performed using ANCOVA (two factor interactions: compliance/noncompliance  $\times$  treatment group) controlled for the baseline value using Bonferroni for multiple comparisons. If the significance of the overall group difference is  $p < 0.05$ , then the effect will be localized by contrast to the Con group. When the 95% CI does not include zero, the difference is regarded as statistically significant at  $\alpha = 0.05$ .

Linear Pearson's correlation, partial correlation, Kendall Tau's, and bivariate, logistic, and multivariate regression analysis will be used for analyzing relationships. In addition, systems biology approaches will be used to develop models which integrate the different types of data and the high-throughput data measured in terms of gut microbiota composition, as well as LPSs and inflammation.

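### Objective 3 is about mediation, but no stated analysis estimates an indirect effect, so a microbiota–glucose association could be reported as mediation

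*Protocol*

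**What the plan says.** Protocol, Objectives, item 3: "To investigate the mediating effect of gut microbiota on glucose control in diabetes and pre-diabetes". The Background gives the same idea as the trial's aim, an effect on glucose "via modification of gut microbiota composition and other post-interventional effects".

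Three kinds of analysis are described in the protocol (Statistical methods), and the SAP (Statistical plans) repeats them almost word for word:

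- Treatment effects: "The effects of the interventions will be assessed using analysis of variance (ANCOVA) for repeated measures", with a group-by-time term and a baseline covariate.
- Associations: "Linear Pearson's correlation, partial correlation, Kendall Tau's, and bivariate, logistic, and multivariate regression analysis will be used for analysing relationships". The SAP adds no detail: "bivariate, logistic, and multivariate regression analysis will be used for analyzing relationships".
- Integration: "systems biology approaches will be used to develop models which integrate the different types of data and the high-throughput data measured". The sentence goes on to mention microbiota composition, LPS and inflammation. It does not name glucose.

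On timing, the protocol (Primary and secondary outcomes) states: "The primary and secondary outcome measures will be assessed at baseline, 1- and 3-month time points". Microbiota composition and blood glucose are both listed there as primary outcomes.

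Mediation is named only in the objective. Neither document gives a mediator variable, an indirect effect, an interval method for one, a set of mediator–outcome confounders, or an order in time between mediator and outcome.

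**The concern.** Mediation is the part of the randomised effect on glucose that passes through a change in the microbiota. It needs two links: treatment must move the microbiota, and the microbiota must in turn affect glucose. ANCOVA on each outcome speaks to the first link and to the total effect on glucose. A correlation or regression between microbiota and glucose speaks at most to the second. The plan never combines them.

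Two false readings follow. First, people whose microbiota differ may differ in glucose for reasons unrelated to the product, so a strong association can exist when treatment leaves the microbiota unchanged. Adjusting for arm does not remove it. Second, if treatment shifts both variables by separate routes, pooling the arms creates a correlation although neither affects the other.

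At stake is one of three stated objectives and the mechanism named in the trial's title. The randomised comparison of glucose is not affected.

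**Working it through.** **The plan's own figure.** The only power figure (Protocol, Sample size estimation) is 68 evaluable per prediabetes group for fasting glucose, raised for 15% drop-out: 68 / (1 - 0.15) = 80, as stated. The 68 cannot be reproduced because no difference or SD is given. Solving backwards at 85% power and alpha 0.05/10 = 0.005 gives a standardised difference of 0.62 (one-sided) to 0.66 (two-sided). No figure is given for mediation.

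**Inputs.** From the documents: 68 per arm for prediabetes. For diabetes, 30 per arm (Trial design) gives 30 × 0.85 = 25.5, taken as 25 evaluable. Assumed, in SD units: a = treatment on microbiota, b = microbiota on glucose, c = direct effect of treatment on glucose. The value a = 0.63 lies within the back-solved range. Tests are at 0.05, with 3,000 simulated trials per scenario and one microbiota index. The indirect effect is a × b with a Monte Carlo 95% interval.

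**Share of trials significant, 68 per arm (25 per arm in brackets)**

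| Scenario | Pooled Pearson | Arm-adjusted regression | Indirect-effect CI |
|---|---|---|---|
| No mediation: a=0, b=-0.4, c=-0.3 | 99% (75%) | 99% (75%) | 5% (4%) |
| No mediation: a=0.63, b=0, c=-0.63 | 18% (10%) | 5% (4%) | 5% (2.5%) |
| No mediation: a=1, b=0, c=-1 | 66% (29%) | 5% (5%) | 5% (5.5%) |
| Mediation: a=0.63, b=-0.4, c=0 | 99.6% (81%) | 99% (76%) | 95% (45%) |
| Mediation, opposed: a=1, b=-0.4, c=+1.2 | 43% (18%) | 99% (77%) | 99% (72%) |

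**Check by hand (68 per arm).** With equal arms and unit residual SDs, Var(M) = 1 + a²/4, Cov(M,Y) = b·Var(M) + ac/4, and Var(Y) = (c + ab)²/4 + b² + 1. Pearson power is about Φ(|atanh r|·√133 - 1.96), where 133 = 136 - 3.

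- Row 1: r = -0.4/√1.1825 = -0.368; 0.386 × 11.53 = 4.45; Φ(2.49) = 99%.
- Row 2: r = -0.0992/1.0992 = -0.090; 1.04; Φ(-0.92) = 18%.
- Row 3: r = -0.25/1.25 = -0.20; 2.34; Φ(0.38) = 65%.
- Row 5: r = -0.2/√(1.25 × 1.32) = -0.156; 1.81; Φ(-0.15) = 44%.

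In row 1 a test needing both paths has rate 0.05 × 0.99, about 5%, because the treatment-to-microbiota path is null.

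**Diabetes precision.** Detection is about Φ(a√(n/2) - 1.96) × Φ(|b|√(2n) - 1.96). At n = 25, a = 0.63, b = -0.4: 0.605 × 0.807 = 49%, a little above the simulated 45%. At a = 0.8: 0.807 × 0.807 = 65%. The Sample size estimation section gives 60 per diabetes group, not 30. With 60 × 0.85 = 51 evaluable and a = 0.63, the result is 0.889 × 0.981 = 87%.

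**Limits of the remedy.** With an unmeasured confounder loading 0.6 on both microbiota and glucose, a = 0.63 and b = 0, the indirect-effect interval was falsely significant in 95% of trials at 68 per arm. With the same confounder masking a real path (b = -0.36), it was significant in only 5%.

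**The case against.** The strongest reply is that the parts are already there. ANCOVA on microbiota gives the first path, and the listed regressions could give the second if glucose were regressed on microbiota, arm and baseline. On that view the plan is under-specified, not wrong. It is true that the parts fit within the listed methods. But neither document says they will be combined, or that arm or baseline will enter the regression. 16S data offer many indices, so a choice made after seeing them is not a test of the objective. Row 1 also shows that the arm-adjusted coefficient alone does not settle mediation.

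It is also fair that the 18% to 66% applies to pooled correlation only; adjusting for arm brings it back to about 5%.

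A reader might infer that the listed methods would also miss real mediation. The documents do not support that. Under plain mediation, pooled correlation and arm-adjusted regression detect the association in 99% or more at 68 per arm, and a correlation of month-1 microbiota with month-3 glucose did so in 93% to 100%. Low detection appears only for some unadjusted correlations under added assumptions. Examples are the 43% in the last row, where a direct effect opposes the mediated one, and change-with-change correlations, which fell from 77–83% under plain mediation to 18–30% with an opposing direct effect of +0.6.

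Finally, mediation models rest on untestable assumptions. This stands, and it argues for stating the assumption and testing sensitivity to it. The planned correlations state no assumption at all.

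**Conclusion.** The concern holds as a mismatch between objective and analysis. As written, the plan yields treatment effects and associations but no indirect effect, so an association could be reported as mediation when there is none. The size under assumed effects at 68 per arm is about 99% against 5% when treatment does not move the microbiota (b = -0.4), and 18% to 66% for a pooled correlation when treatment moves both separately by 0.63 to 1 SD. These rates rest on linear models, a single microbiota index and effect sizes that the documents do not supply. The direction is sound, but the exact percentages will vary.

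To say that the objective cannot be answered by any listed method would go too far, since the two component regressions could be built from the list. The point deserves correction but does not threaten the primary treatment comparison.

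**What to change.** For each population, write into the SAP:

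1. One microbiota summary, chosen in advance, at month 1 as mediator, and month-3 fasting glucose as outcome.
2. Two models: mediator on treatment, and outcome on mediator plus treatment. Adjust both for baseline microbiota and baseline fasting glucose.
3. The indirect effect with a bootstrap 95% confidence interval.
4. A sensitivity analysis for unmeasured mediator–outcome confounding, with the assumption stated.
5. A sentence labelling the correlations as descriptive.

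The visits already supply the data, so the cost is one extra analysis per population. There are three downsides. The causal reading depends on no unmeasured mediator–outcome confounding, which the trial cannot verify. A single summary may not carry the taxa that respond to treatment. In diabetes the estimate will be imprecise: detection is between about 45% and two-thirds at 25 evaluable per arm for the assumed shifts of 0.63 to 0.8 SD. It should be reported there as an estimate with its interval, not as a test. The two planned diabetes sizes, 30 per group under Trial design and 60 under Sample size estimation, must also be reconciled.

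### DNA from the dead S. thermophilus in the product can register as a change in gut composition on fecal 16S sequencing, and the plan has no rule for product reads

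*Protocol*

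**What the plan says.** - **Product.** Protocol, Interventions, item 1: "each pack contains 880 billion dead" Lactobacillales, named as S. thermophilus. Participants "take four packs of probiotics a day on an empty stomach with 200ml water every morning".
- **Placebo.** Protocol, Interventions, item 2, repeats the same dosing sentence, including the word probiotics. The placebo's content is not given anywhere.
- **Outcome.** Protocol, Primary and secondary outcomes, lists "Gut microbiota composition" as the second primary outcome, and adds: "The primary and secondary outcome measures will be assessed at baseline, 1- and 3-month time points".
- **Assay.** Protocol, Methods of measurements, item 3 (fecal samples): "16SrDNA sequencing will be performed". Unspecified bacterial indices are then to be calculated.
- **Timing.** Protocol, Trial design, describes an "intervention study for a total duration of 3 month". Month 1 is on product, month 3 is at the end of dosing, and no later stool sample is planned.
- **Outside bacterial products.** Exclusion criterion 5, "Take antibiotics or bacterial agents within 1 month", applies at entry. It does not bear on the study product at months 1 and 3.
- **Analysis.** Protocol, Statistical methods, and the SAP give repeated-measures ANCOVA, correlation and regression methods, and systems-biology modelling. Neither defines a composition metric or says how reads matching the product are handled.

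**The concern.** 16S sequencing amplifies bacterial DNA whether or not the cell was alive. Because the product organisms are dead, extra S. thermophilus reads during treatment cannot be colonisation by the product; they may simply be product in transit. If the placebo does not contain the organism, those reads enter one arm and not the other.

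There are two routes to a misleading composition result. The product's own taxon rises. And if the indices use relative abundances, which sum to one, every other taxon falls in proportion with no change in the resident community.

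At stake is the interpretation of a primary outcome: a difference between arms could be detection of the product. Objective 3, which asks whether the microbiota mediates glucose control, is exposed too. A mediator containing product reads partly measures treatment received and doses taken.

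**Working it through.** The plan states no figure for product reads, so there is none to reproduce. The check is whether the premises hold and how large the effect could be.

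**Inputs from the Protocol**
- Organisms per pack: 880 billion, dead (one cell each is implied, not written).
- Packs per day: 4.
- Stool samples: baseline, month 1 and month 3 of a 3-month intervention.

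**Daily dose**
D = 4 x 880 x 10^9 = 3.52 x 10^12 per day.

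**Assumptions, none of them in the documents**
- L, resident bacteria shed per day: 10^12 to 3 x 10^13.
- s, fraction of product DNA still amplifiable in stool: 0.1% to 10%.
- Equal 16S copies per cell for product and resident bacteria.

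**Formulas**
Product share of reads = D s / (D s + L). Every other taxon's relative abundance is multiplied by 1 - share.

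| L per day | s = 0.1% | s = 1% | s = 10% |
|---|---|---|---|
| 10^12 | 0.35% | 3.4% | 26% |
| 10^13 | 0.035% | 0.35% | 3.4% |
| 3 x 10^13 | 0.012% | 0.12% | 1.2% |

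Worked cells:
- Low corner: D s = 3.52 x 10^9; 3.52 x 10^9 / (3.52 x 10^9 + 3 x 10^13) = 0.012%. Other taxa are practically unchanged (x 0.9999).
- Middle: D s = 3.52 x 10^10; 3.52 x 10^10 / (3.52 x 10^10 + 10^13) = 0.35%. Other taxa x 0.9965.
- High corner: D s = 3.52 x 10^11; 3.52 x 10^11 / (3.52 x 10^11 + 10^12) = 26%. Other taxa x 0.74.

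Wider assumptions widen the answer. With L = 10^14 and s = 0.01% the share is 0.0004%; with L = 10^12 and s = 100% it is 78%. The effect may be negligible or large, and the documents do not settle which.

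**What the plan has in place**
Neither document mentions removal of product-matching reads, a strain-specific count, an assay selective for living cells, a stool sample after a product-free interval, or a sensitivity analysis without the product taxon.

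**Mediation**
An indirect effect needs two links: treatment to mediator, and mediator to glucose given treatment. Product reads create or inflate the first. They do not by themselves create the second. That needs a further path, for instance adherence that raises product reads and is also related to glucose.

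**The case against.** The strongest reply is that the size rests entirely on assumed inputs and is small over most of the grid. In the middle case other taxa shrink by 0.35%, which would hardly move a community-level index, and the artefact would sit in one taxon that an informed reader would recognise as the product. This stands as a limit on size. It does not remove the need for a rule, because the plan has no means of showing which part of the grid applies.

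A reader might infer four stronger things that the documents do not support:

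- **That the bias certainly falls in one arm.** The placebo's content is not described and its dosing sentence also refers to probiotics. This may be a drafting slip, but the between-arm artefact is conditional on a placebo free of the organism. If both arms received it, the product signal would tend to cancel between arms.
- **That even the low end gives a clear arm difference.** A share of 0.012% is about one read in 10,000. Sequencing depth, low-abundance filtering and the baseline level of this taxon are not stated, so that does not follow.
- **That the mediation analysis is biased towards a false positive.** Transit DNA alone supplies only one of the two links. Without a further mechanism it adds noise to the mediator.
- **That the plan has decided to keep product reads.** It is silent; no composition metric is defined at all. The fair statement is that their handling is unspecified.

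It can also be argued that an unfiltered primary analysis with a pre-specified sensitivity analysis answers the same question. That is reasonable, provided the claim of a community change depends on the filtered result.

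**Conclusion.** The point holds in conditional form. The dose of 3.52 x 10^12 dead organisms a day, the primary status of composition, the fecal 16S assay, sampling during or at the end of dosing, and the absence of any rule for product reads are all in the documents. If the placebo lacks the organism, the plan as written can count swallowed product as a change in gut composition.

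The size is unknown: about 0.01% to 26% of reads under the assumed ranges for fecal output and DNA recovery. The direction is clear for the product's own taxon and, on a relative scale, for the others; for a summary index it depends on a metric not yet defined. For mediation, the treatment-to-mediator link is contaminated, and the result could mislead if adherence is also related to glucose.

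The glucose outcomes are unaffected, as is the sample size for the prediabetes groups, whose stated power is for fasting glucose. This should be corrected in the SAP, but it is not a fatal flaw.

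**What to change.** 1. Pre-specify the composition analysis with reads assigned to the product taxon removed, and the rest renormalised, before indices or distances are calculated. Filter at species level, or at Streptococcus if 16S cannot resolve the species.
2. Report the unfiltered analysis beside it, and claim a change in the gut community only if it holds in the filtered analysis.
3. Report product-taxon reads separately, as an exposure marker, and keep that taxon out of the mediator for Objective 3.
4. State what the placebo contains and reconcile its dosing text with its description as a placebo.

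The cost is one filtering step in the bioinformatics and a few lines of SAP text; no dose, visit or sample size changes. The downside is that genus-level filtering discards some resident Streptococcus reads, possibly including a real change. Showing both analyses keeps that visible.
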